Secondary Aim #4. Among participants with PAD, we will determine whether NR alone improves maximal treadmill walking time, the WIQ distance score, and physical activity at 6-month follow-up, compared to placebo. *We hypothesize that participants randomized to NR alone will have greater improvement or less decline in maximal treadmill walking time, the WIQ distance score, and physical activity at 6-month follow-up, compared to those randomized to placebo.*

Secondary Aim #5. Among participants with PAD, we will determine whether NR combined with resveratrol improves maximal treadmill walking time, the WIQ distance score, and physical activity at 6-month follow-up, compared to placebo. *We hypothesize that participants randomized to NR plus resveratrol will have greater improvement or less decline in maximal treadmill walking time, the WIQ distance score, and physical activity at 6-month follow-up, compared to those randomized to placebo.*

Secondary Aim #6. Among participants with PAD, we will determine whether those randomized to NR + resveratrol have greater improvement in each outcome defined in Secondary Aims #4 and #5, compared to those randomized to NR alone. *We hypothesize that participants randomized to NR combined with resveratrol will improve each outcome at 6-month follow-up, compared to NR alone.*

Secondary Aim #7. Participants with PAD who received NR alone and those who received NR + resveratrol will be combined into one group and compared to the group receiving placebo, to determine whether NR alone or NR + resveratrol (combined group) have greater improvement in six-minute walk distance at 3-month follow-up and at 6-month follow-up, compared to those randomized to placebo. *We hypothesize that the combined NR group will improve six-minute walk distance at 3-month follow-up and at 6-month follow-up, compared to placebo.*

Secondary Aim #8. Participants who received NR alone and those who received NR + resveratrol will be combined into one group and compared to the group receiving placebo, to determine whether those randomized to NR alone or NR + resveratrol (combined group) have greater improvement in maximal treadmill walking time, the WIQ distance score, physical activity, and calf muscle biopsy measured NAD+ abundance, satellite cell abundance, and muscle fiber phenotype, compared to the placebo group. *We hypothesize that the combined NR group will improve each outcome at six-month follow-up, compared to placebo.*

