Exploratory Aim #1. We will perform calf muscle biopsies to determine whether among participants with PAD, those randomized to NR + resveratrol or NR alone have increased calf muscle NAD+ abundance, increased satellite cell abundance and improved muscle fiber phenotype, compared to the placebo group. We hypothesize that PAD participants randomized to either NR+ resveratrol or NR alone will achieve increases in each of these measures,

compared to those randomized to placebo. Additional calf muscle measures will be assessed in Specific Aim #1 of a separate project funded as part of this American Heart Association Strategically Funded Research Network (SFRN) (PI: [name], PhD).

Exploratory Aim #2. Among participants with PAD, we will determine whether NR alone improves the WIQ speed and stair climbing scores and the Short-Form Physical Functioning score at 6-month follow-up, compared to placebo.

Exploratory Aim #3. Among participants with PAD, we will determine whether NR combined with resveratrol improves the WIQ speed and stair climbing scores and the Short-Form Physical Functioning score at 6-month follow-up, compared to placebo.

Exploratory Aim #4. Among participants with PAD, we will determine whether NR combined with resveratrol improves the WIQ speed and stair climbing scores and the Short-Form Physical Functioning score at 6-month follow-up, compared to NR alone.

Exploratory Aim #5. Participants who received NR alone and those who received NR + resveratrol will be combined into one group and compared to the group receiving placebo, to determine whether those randomized to NR alone or NR + resveratrol (combined group) have greater improvement in the WIQ speed and stair climbing scores and the Short-Form Physical Functioning score at 6-month follow-up, compared to placebo.

STUDY INVESTIGATIONAL AGENTS:

Participants will be randomized to one of three groups: NR + resveratrol, NR + placebo, or placebo + placebo. Chromadex will supply the NR and matching placebo to the Northwestern Medicine Investigational Pharmacy. Reserveage Organics will supply resveratrol and matching placebo to the Northwestern Medicine Investigational Pharmacy.

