Power and Sample Size Estimation. We will enroll 30 patients per group. Based on our experience with randomized trials in PAD, we anticipate that 27 participants in each group will complete 6-month follow-up and provide outcomes for the statistical analysis (44,74). For Primary Aim 1, we will use a two-sample t-test to compare the 6-month decline in six-minute walk distance between NR alone and placebo. Twenty-seven participants per group provides 80% power for detecting a difference of 0.69 standard deviation (SD) of the decline at the one-sided significance level of 0.1. Based on our GOALS Trial results (74), a 0.58 SD represents a difference of 30 meters in six-minute walk distance. Similarly, for Primary Aim 2, we will have 80% power for detecting a difference of 30 meters between NR combined with resveratrol vs. placebo. For Secondary Aim #1 and Secondary Aim #2, we will have 80% statistical power for detecting a difference of 30 meters between the NR alone vs. placebo group (Secondary Aim #1) and between the NR combined with resveratrol group vs. the placebo group (Secondary Aim #2) at 3-month follow-up. In our Secondary Aim #3, we will have 80% statistical power for detecting a difference of 30 meters between the NR combined with resveratrol group and the NR alone group at 3-month and at 6-month follow-up. Most prior studies have defined clinically meaningful changes in the six-minute walk as 20-50 meters (77-80). Thus, the study has sufficient statistical power for detecting a clinically meaningful difference under the same assumptions. The NICE Trial is a proof of principle study intended to collect evidence for a large randomized trial. For Secondary Aim #4, we will compare changes in maximal treadmill walking distance, the WIQ distance score and physical activity between NR alone vs. placebo. The study provides 80% power for detecting a difference of 0.58 SD. Similarly, in Secondary Aim #5, we will compare changes in maximal treadmill walking distance, the WIQ distance score and physical activity between NR + resveratrol and placebo. In our GOALS trial, 0.69 SD of 6-month decline in WIQ represented a difference of 14 points for the WIQ distance score (74). The difference in reported cut-off values in WIQ scores between high and low PAD performers is 76 minus 43, or 33 points (83). Therefore, the study should have sufficient statistical power for detecting clinically important differences in the WIQ distance score. For Secondary Aim 6, we will compare 6-month changes in maximal treadmill walking distance, the WIQ distance score, and physical activity between people randomized to NR combined with resveratrol, compared to NR alone. For Secondary Aim 7, we will compare 3-month and 6-month changes in six-minute walk distance between all people randomized to an NR group (i.e. those randomized to NR combined with resveratrol and those randomized to NR alone) and those randomized to placebo. For Secondary Aim 8, we will compare 6-month changes in maximal treadmill walking time, the WIQ distance score, and physical activity between all people randomized to an NR group (i.e. those randomized to NR combined with resveratrol and those randomized to NR alone) and those randomized to placebo. In Secondary Aims #7 and #8, we have 80% power for detecting a difference of 0.50 SD. The proposed mixed effects regression analysis has a higher power than the two-sample t-test and thus can detect even smaller differences.

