
Statistical Analyses. Analyses will be performed using the intention to treat principle. Prior to the analyses, the distributions of the variables (changes) will be examined. For our Primary Aim #1, we will use a mixed effects repeated measurements (MMRM) regression to compare changes in six-minute walk performance at 6-month follow-up between the NR alone vs. placebo groups, adjusting for age, sex, race, and baseline six-minute walk distance. Age, sex,

and race will be adjusted for because of their association with change in six-minute walk distance (see below). Similar analyses will be performed for Secondary Aims #1, #2, #3, and #7. For our Primary Aim #2, we will use a one-tailed t-test based on MMRM to compare changes in six-minute walk between NR combined with resveratrol vs. placebo. We will perform MMRM regression analysis with the change in six-minute walk distance at month 3 and month 6 as the correlated response variable with an unstructured covariance matrix to evaluate differences in change in six-minute walk distance between the two groups in each comparison, adjusting for potential baseline confounders specified as following: baseline six-minute walk performance, age, sex, and race. The mixed effect regression would include patients missing the 6 month follow-up visit, assuming missing at random. If either primary aim is positive, the clinical trial will be considered positive. A one-sided P value at $P<0.10$ will be considered statistically significant. We are selecting this P value because of the preliminary (pilot) nature of this work. For Secondary Aims #4, #5, #6, #8 and Exploratory Aims, we will use the analysis of covariance to compare the 6-month change of each outcome, separately. In each specific comparison, the baseline value for the outcome of interest (i.e. WIQ score, treadmill, physical activity) will be adjusted for (rather than the six-minute walk) in addition to age, sex and race. For the Secondary Aims #7 and #8, the NR + placebo groups will be combined with NR + resveratrol into one group and compared to the placebo group and the MMRM regression or analysis of covariance will additionally adjust for the resveratrol usage.

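### Secondary Aims 7 and 8 pool both NR arms against placebo, but an undefined resveratrol adjustment, if coded 0/1, turns the Aim 8 contrast into NR alone versus placebo and its detectable difference from 0.50 to 0.58 SD

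*Combined protocol and SAP*

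**What the plan says.** The Study Endpoints section defines Secondary Aims 7 and 8 by merging the NR alone and NR + resveratrol arms and comparing them with placebo. The Aim 7 hypothesis is that "the combined NR group will improve six-minute walk distance at 3-month follow-up and at 6-month follow-up, compared to placebo". The Aim 8 hypothesis is that "the combined NR group will improve each outcome at six-month follow-up, compared to placebo". Power and Sample Size Estimation describes the same pooled comparison and states: "In Secondary Aims #7 and #8, we have 80% power for detecting a difference of 0.50 SD". For Secondary Aim 4, which compares NR alone with placebo, the same section states: "The study provides 80% power for detecting a difference of 0.58 SD".

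Statistical Analyses repeats the pooling for Aims 7 and 8 and then adds that "the MMRM regression or analysis of covariance will additionally adjust for the resveratrol usage". No definition, coding or reported contrast follows. The later list of mixed-model terms (treatment, visit, treatment by visit, baseline walk distance, age, sex, race) contains no resveratrol term, either alone or by visit.

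Exploratory Aim 5 asks whether the same combined group will "have greater improvement in the WIQ speed and stair climbing scores" and in physical functioning. The resveratrol adjustment is not prescribed for it.

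**The concern.** The three arms are placebo, NR alone and NR + resveratrol, so resveratrol is given only on top of NR. Exclusion criterion 15 removes people who take resveratrol or took it in the previous six months. Resveratrol usage is therefore most naturally a 0/1 marker of the NR + resveratrol arm. A model with an NR indicator and that marker does not pool the NR arms. It separates them again, and the NR coefficient describes the NR alone arm.

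Three things are at stake.

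- **Aim 8 would not test its own hypothesis.** For treadmill time, WIQ distance and physical activity it would repeat Aim 4. The arm that the Objectives section expects to be particularly potent would drop out of the contrast.
- **The power statement would describe a different analysis** from the one prescribed.
- **One label would cover two estimands.** WIQ distance (Aim 8, adjusted) and WIQ speed and stair climbing (Exploratory Aim 5, unadjusted) would both be reported as combined group versus placebo.

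**Working it through.** **Inputs.** 27 completers per arm and one-sided alpha 0.10 (Power and Sample Size Estimation; the alpha is repeated in Statistical Analyses). Normal quantiles: 1.2816 (90%) and 0.8416 (80%), sum 2.1232. Effects are in SD of the change score, with no covariate gain at this stage.

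**1. Reproduce the plan's figure (no resveratrol term, 54 versus 27).**
- SE = sqrt(1/54 + 1/27) = sqrt(1/18) = 0.2357
- Detectable difference = 2.1232 × 0.2357 = 0.500 SD
- Power at 0.50 SD = Φ(0.50/0.2357 − 1.2816) = Φ(0.840) = 79.9%

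The noncentral t version gives 0.503 SD and 79.6%. The stated 0.50 SD is therefore the plain pooled comparison.

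**2. What a 0/1 term does in the Aim 8 analysis of covariance.** With equal arms, the NR coefficient equals the pooled contrast minus half the estimated resveratrol increment:

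[½(NR alone) + ½(NR + resveratrol) − placebo] − ½[(NR + resveratrol) − (NR alone)] = NR alone − placebo.

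The weights on (placebo, NR alone, NR + resveratrol) are (−1, +1, 0).
- Variance = 1/18 + ¼ × 2/27 = 2/27, which is 4/3 of the pooled variance; SE = 0.2722
- Detectable difference = 2.1232 × 0.2722 = 0.578 SD
- Power at 0.50 SD = Φ(0.50/0.2722 − 1.2816) = Φ(0.556) = 71.1%

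The noncentral t version gives 0.581 SD and 70.7%. The 0.578 SD matches the 0.58 SD that the plan gives for Aim 4, as it should, since the contrast is the same.

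**3. A coding that would not do this.** Code resveratrol +0.5 and −0.5 within the two NR arms and 0 in placebo. The NR weights become (−1, 0.5, 0.5), the variance is 1/18 and the detectable difference stays at 0.500 SD. Coding −1/+1 across all three arms, or centring the 0/1 indicator on its overall mean, still gives (−1, +1, 0).

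**4. The Aim 7 mixed model (months 3 and 6).**
- *Resveratrol by visit:* identical to step 2 at each visit.
- *Resveratrol main effect only:* the month-6 NR estimate is the month-6 pooled contrast minus ½ of a common increment estimated from both visits. If the true increment is constant over visits, this is again NR alone minus placebo.
- *Main effect only, increment not constant:* the estimate is a mixture. Assuming equal variances at the two visits, an increment δ present only at month 6 leaves 0.25δ in the month-6 estimate; pooling would keep 0.50δ. Assuming a correlation of 0.4 to 0.8 and a month-3 variance of 0.5 to 1.0 times that of month 6, the retained share runs from 0.25 to 0.59. The variance is 1.15 to 1.30 times the pooled value, so the detectable difference is 0.54 to 0.57 SD and power at 0.50 SD is 76% to 72%. The documents give none of these inputs.

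**5. Illustration of the change in estimand (assumed effects, no covariates, Aim 8).** Suppose NR alone has no effect and NR + resveratrol has 0.58 SD. The pooled mean difference is 0.29 SD, and the three-arm pooled contrast rejects with probability Φ(0.29/0.2357 − 1.2816) = 48%. The 0/1-adjusted test rejects at its alpha, 10%. With the effects reversed, the figures are 48% and Φ(0.58/0.2722 − 1.2816) = 80%.

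**The case against.** The strongest reply is that the plan contains an undefined term, not a demonstrably wrong model. That stands in part: step 3 shows a coding that keeps both the adjustment and the 0.50 SD. A reader might infer that 0.50 SD cannot hold with any resveratrol term in the model. The documents do not support that; the result is conditional on 0/1 coding. But 0/1 is the ordinary coding for such a variable, and the plan states neither another coding nor a linear combination that would recover the average of the two arms.

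A second reply is that the power figure rests on a two-sample t-test, and the plan says: "The proposed mixed effects regression analysis has a higher power than the two-sample t-test and thus can detect even smaller differences". Covariates may indeed recover precision. Full recovery in Aim 8 requires them to explain 1 − (1/18)/(2/27) = 25% of the variance of the change score. The documents give no such figure for the Aim 8 outcomes. For the six-minute walk, the correlation of 0.812 between baseline and follow-up distance does not give the share of change explained unless the SD ratio is also known. A reader might infer that Aims 7 and 8 fall short of 80% power, or that the term costs a fixed number of points in every model. Neither is shown. What stands is that covariates cannot restore the pooled contrast.

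Third, usage might mean actual intake, including off-protocol use after randomization, which the entry exclusion does not rule out. That reading would also need a definition, and it would put a post-randomization variable in the model.

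Fourth, the scenarios in step 5 are extremes. With equal effects of 0.5 SD in both NR arms, the two analyses estimate the same value and differ only in precision (71% versus 80% before covariates).

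**Conclusion.** The point holds, conditional on coding. If resveratrol usage is a 0/1 indicator of the NR + resveratrol arm, the Aim 8 analysis estimates NR alone versus placebo instead of the pooled contrast its hypothesis names. The detectable difference before covariate gain is then 0.578 SD instead of 0.50 SD (71.1% instead of 79.9% power at 0.50 SD). This rests on 27 completers per arm and one-sided alpha 0.10, both from the plan.

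A reader might infer that Aim 7 collapses in the same way. It does so only if the term interacts with visit, or if the resveratrol increment is constant over time. With a main effect only, it is otherwise a mixture whose weights the documents do not fix.

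The practical reach is limited. Aims 7 and 8 are secondary aims of a pilot trial. Both primary aims, and the rule that either one makes the trial positive, are untouched. All pairwise comparisons of the functional outcomes are specified separately. The wording should be corrected because two analysts following it could report different estimands under one name.

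**What to change.** For Secondary Aims 7 and 8 only, take one of these two routes:

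- delete the resveratrol-usage adjustment and use a single combined-group indicator, by visit in the mixed model; or
- fit the three-arm model and pre-specify 0.5 × (NR alone) + 0.5 × (NR + resveratrol) − placebo at each visit.

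Either route matches the stated hypotheses and the 0.50 SD figure, and brings Aim 8 into line with Exploratory Aim 5.

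If the intention was to isolate NR from resveratrol, define usage and its coding, restate both aims as NR alone versus placebo, and restate the detectable difference as 0.58 SD. In that case, note that Primary Aim 1 and Secondary Aims 1 and 4 already cover that contrast for the functional outcomes.

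The first two routes cost one sentence of analysis-plan wording. The third also means rewording the aims and the power statement. None needs new data or participants.

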For all of the analyses, The MMRM regression includes treatment indicator, visit time (month 3 and month 6 as categorical factors), the interactions between treatment and visit time, baseline six minute walking distance (for all aims in which six-minute walk is the outcome), age, sex and race. For comparisons of other endpoints not measured longitudinally, the conventional analysis of covariance will be used adjusting for the baseline level of the corresponding outcome, age, sex, and race. We will adjust for baseline six-minute walk, age, sex, and race, because these variables have been correlated significantly with either change in six-minute walk or with six-minute walk at follow-up in our prior studies. For example, in the combined data from the control groups of our GOALS, LITE, PROPEL, and TELEX randomized clinical trials of exercise interventions for people with PAD, six-minute walk at baseline was correlated with six minute walk distance at six-month follow-up (Pearson correlation coefficient= 0.812, $P<0.001$). In addition, participants who were Black had significantly poorer six-minute walk, compared to those who were not Black, at six-month follow-up (320.9 meters (SD: 104.5) vs. 359.8 meters (102.5), $P=0.0035$). Women had significantly poorer six-minute walk, compared to men, at six-month follow-up (309.6 (SD: 103.2) vs. 358.7 (SD: 102.1), $P<0.001$). In our observational WALCS cohort of men and women with PAD, older age was associated significantly with greater decline in six-minute walk distance at one-year follow-up (correlation= -0.236, $P<0.001$).

In a sensitivity analysis, we will repeat all comparisons additionally adjusting for baseline covariates that show major imbalances between relevant treatment groups, where the major imbalance is defined as Cohen's effect size being greater than 0.5. The MMRM analysis for comparing the change in six-minute walking distance will be based on all participants who have their six minute walking distance measured at least once during follow-up (i.e. at least at month 3 or month 6).

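### If the baseline-walk slope differs between month 3 and month 6, the MMRM's single slope slightly under-adjusts the primary month-6 contrast; a baseline-by-visit term removes this almost free

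*Combined protocol and SAP*

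**What the plan says.** In the combined protocol and SAP, under Statistical Analyses, the response is "the change in six-minute walk distance at month 3 and month 6 as the correlated response variable with an unstructured covariance matrix". The fixed effects start with a treatment indicator and categorical visit. The list goes on with "the interactions between treatment and visit time, baseline six minute walking distance", and three demographic covariates (age, sex, race) complete it. Read as a list, this contains one interaction, treatment by visit, and enters baseline walk as a main effect. Nothing else in the section relaxes that. The sensitivity analysis adds covariates with an imbalance above 0.5 in Cohen's effect size, but no covariate-by-visit term.

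On missing data: "The mixed effect regression would include patients missing the 6 month follow-up visit, assuming missing at random". The analysis set is "all participants who have their six minute walking distance measured at least once during follow-up".

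To justify adjusting for baseline, the same section reports from pooled control groups of earlier exercise trials that "six-minute walk at baseline was correlated with six minute walk distance at six-month follow-up", with a coefficient of 0.812. No figure is given for month 3.

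**The concern.** The model leaves the covariance unstructured and lets the treatment effect differ by visit, yet holds the slope on baseline walk constant over visits. A walk repeated after three months may well track baseline more closely than one repeated after six. The slope of change on baseline would then be flatter at month 3 than at month 6. A common slope lies between the two, so part of the baseline effect at month 6 stays unadjusted.

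When the arms are balanced on baseline among those observed, this does no harm on average. It matters when losses leave the arms different on baseline at month 6, because likelihood-based analysis under missing at random relies on a correctly specified mean model. Month 6 is the primary time point for both primary aims.

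**Working it through.** **1. The plan's own figures.** Power and Sample Size Estimation states 80% power with 27 per group at one-sided 0.10. By normal approximation, power = Φ(d√(27/2) − 1.2816).
- d = 0.58: Φ(2.131 − 1.282) = 80.2% (noncentral t 79.8%).
- d = 0.69: Φ(2.535 − 1.282) = 89.5% (noncentral t 89.1%).

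So 0.58 SD, which the section equates with 30 m, is the value that fits the stated alpha. It gives an SD of change of 30/0.58 = 51.7 m. The mismatch between 0.69 and 0.58 is a separate matter, and this point does not depend on it.

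**2. Slopes of change on baseline.** With equal SDs at each visit (assumed), slope = r − 1.
- Month 6, stated r = 0.812: slope −0.188.
- Month 6, from the power section, with an assumed level SD of 104 m (the plan's month-6 subgroup SDs are 102.1 to 104.5 m): r = 1 − 51.7²/(2 × 104²) = 1 − 2,673/21,632 = 0.876, slope −0.124.
- These two sources disagree: r = 0.812 would give an SD of change of 104 × √(2 × 0.188) = 63.8 m. Both are carried forward.
- Month 3, assumed r = 0.86, 0.90, 0.93: slopes −0.14, −0.10, −0.07. Equal slopes are kept as the null case.

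**3. Mechanism.** To a first approximation, bias = (month-6 slope − common slope) × (baseline difference between arms among those seen at month 6).

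A large-sample check used 400,000 per arm, slopes −0.10 and −0.188, assumed residual SDs 50 and 60 m with correlation 0.8, and 10% loss:
- Loss tied to baseline in one arm: (−0.188 + 0.107) × 9.3 = −0.75 m. Fitted difference, plan minus interaction model: −0.53 − 0.28 = −0.81 m.
- Loss at opposite ends in the two arms: (−0.188 + 0.106) × 19.3 = −1.58 m. Fitted: −1.76 + 0.11 = −1.65 m.

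The sign depends on which arm loses the poorer walkers.

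**4. At trial size.** Simulations used 30 per arm, about 10% loss by month 6 and a level SD of 104 to 105 m; the re-derivation with both models fitted to the same data left out age, sex and race. Size of the mean difference between the plan's model and the interaction model, with the spread over repeat simulations where available:

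| Month-6 r | Month-3 r (assumed) | One-arm loss | Opposite loss |
|---|---|---|---|
| 0.812 | 0.812 | 0 m | 0 m |
| 0.812 | 0.86 | 0.4–0.5 m | 0.7–0.9 m |
| 0.812 | 0.90 | 0.8–0.9 m | 1.4–1.7 m |
| 0.812 | 0.93 | 1.1 m | 2.0–2.1 m |
| 0.876 | 0.90 | 0.2 m | 0.3 m |
| 0.876 | 0.93 | 0.5 m | 1.0 m |

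The interaction model was unbiased within simulation error throughout. When loss was unrelated to baseline, or related in the same way in both arms, the bias was 0 m. At 20% loss with a month-3 slope of −0.10 and a month-6 slope of −0.188, the differences rise to about 1.4–1.6 m and 2.9–3.1 m.

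**5. Error rates** (slopes −0.10 and −0.188, nominal 0.10 in each tail, simulation error about 0.005), plan versus interaction model:
- One-arm loss: upper tail 0.106 vs 0.111, lower tail 0.112 vs 0.100.
- Opposite loss: upper tail 0.077 vs 0.093, lower tail 0.122 vs 0.103.

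**6. Precision.** Under random loss with month-6 r = 0.812, RMSE for the plan versus the interaction model was 16.54 vs 16.52 m (month-3 r = 0.86), 16.66 vs 16.51 m (0.90) and 16.78 vs 16.33 m (0.93). With equal slopes, the empirical SD was 15.06 vs 15.17 m, so an unneeded term costs under 1%.

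**The case against.** The strongest reply is that nothing in the documents shows the slopes to differ. No month-3 correlation, slope or SD is given. With equal slopes the plan's model is correctly specified and unbiased even when the arms lose opposite ends of the baseline range (simulated difference −0.03 m, simulation error 0.05 m). This stands. A reader might infer that the constraint makes the mean model wrong, or defeats the missing-at-random analysis; the documents support neither as a statement of fact.

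Second, the loss patterns are demanding. Ten percent is three people per arm. Blinding, the adherence run-in, follow-up of those who stop the pills, and the allowance for late final visits all work against losses that differ by arm. This also stands; the documents say nothing about loss by baseline or by arm.

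Third, single-trial estimates from the two models differ by about 1.1 to 2.7 m on average under random loss at month-6 r = 0.812. It is tempting to read that as chance imbalance being corrected. Part of it is estimation noise: the models differ by 0.7 to 0.9 m on average even with equal slopes. The RMSE gain, about 0 to 3%, is the fairer measure.

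What the reply does not remove is that the term costs almost nothing and protects the primary contrast if the slopes do differ.

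**Conclusion.** The point holds as a conditional, minor improvement. The listed model imposes one baseline slope, and no other text relaxes it. Two conditions are needed for bias at month 6: slopes that differ by visit, and loss that depends on baseline differently by arm. If either fails, the bias is 0 m.

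If both hold, at 10% loss it is about 0.4 to 2 m with the stated 0.812 and an assumed month-3 correlation of 0.86 to 0.93. It is about 0.2 to 1.0 m with a month-6 correlation near 0.876. Against a standard error of 14 to 17 m, the upper end is at most about 2/14 = 0.14 standard errors, and 2/30 = 7% of the 30 m target. This would rarely change the trial's conclusion, and its direction cannot be predicted. The sizes rest on assumed month-3 correlations, equal SDs over visits and assumed residual SDs.

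**What to change.** In the MMRM specification under Statistical Analyses, add baseline six-minute walk by visit for every aim with six-minute walk as the outcome (Primary Aims 1 and 2; Secondary Aims 1, 2, 3 and 7). The terms become treatment, visit, treatment × visit, baseline walk, baseline walk × visit, age, sex and race, with unstructured covariance. Secondary Aim 7 keeps its existing adjustment for resveratrol use.

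The cost is one sentence in the plan and one degree of freedom, with no new data and RMSE at most about 1% higher. Fixing the term in advance also avoids a later choice between two fits that can differ by a few metres in a single trial.
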